3. N/A

II. Research Plan and Design

- A. Study Objectives:** The objective of this study is to determine if use of liposomal bupivacaine (Exparel) decreases postoperative pain at the donor site compared to lidocaine for split thickness skin grafting in patients with burn injuries. In addition, we aim to identify if use of Exparel at the donor site for split thickness autografting decreases opioid pain medication consumption postoperatively compared to use of lidocaine at the donor site in patients with burn injuries.
- B. Study Type and Design:** This study will be a prospective, randomized controlled trial. Study subjects will be blinded to their randomization to avoid bias. The control group will undergo split thickness autografting using the standard protocol, involving injection of lidocaine with epinephrine at the donor site. The experimental group will undergo injection of liposomal bupivacaine (Exparel) at the time of harvest of the skin graft. Baseline pain levels will be obtained for all subjects using a validated pain assessment scale, the

Visual Analog Pain Scale. Postoperatively, time to first opioid pain medication (excluding immediate postoperative recovery from anesthesia), total opioid consumption on a daily basis, and donor site interval pain scores using a validated pain assessment scale will be obtained. The experimental group will then be compared to the control group to determine if there is a significant difference in pain levels, time to first opioid, and overall opioid consumption between the two groups.

C. Sample size, statistical methods, and power calculation

[figure not shown]
1. Patients will be randomized using a computerized random number generator with 1:1 randomization. Differences between groups will be assessed using Chi square test for categorical variables and Student's t test for two means. Confidence intervals will be calculated to 95% and a p value of less than 0.05 will be considered statistically significant.
2. Only subjects will be blinded to their randomization group. Study subject number will be linked to their randomization group. Blinding may be broken if the subject experiences an adverse reaction to the medication utilized for their group so that they are aware that they cannot receive the medication in the future.

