- 4. Describe how the lead investigators will ensure that all participating sites use the IRB-approved version of the protocol, consent, recruitment materials and other study documents. N/A
- 5. Describe how the lead investigators will communicate with and disseminate new information to other sites (e.g., training meetings, regularly-scheduled conference calls, notifications, etc.) N/A
- 6. Describe how the lead investigator will assess protocol compliance, unanticipated problems and adverse events at other sites. N/A
- 7. Name the member of the KUMC study team who will be the point of contact to coordinate oversight and communication with the sites. N/A

J. Community-Based Participatory Research (if applicable): N/A

- 1. Participants and the nature of their involvement: N/A
- 2. Cultural issues: N/A
- 3. Origin of the research question: N/A
- 4. Risks and Benefits: N/A
- 5. Study Description and Process: N/A
- 6. Return of results: N/A
- 7. Sustainability: N/A

K. Personnel who will conduct the study, including:

- 1. Indicate, by title, who will be present during study procedure(s):

Study personnel may be involved in the study procedures, including patient consent, assignment of study group, and accessing of the patient's medical record to obtain information related to opioid administration

Administration of liposomal bupivacaine or lidocaine will be by an attending burn surgeon or their designated resident, physician's assistant, or nurse practitioner

Pain scale assessment will be completed by the patient's bedside nurse (RN)

- 2. Primary responsibility for the following activities, for example:

- a. Determining eligibility: study coordinator, PI, co-investigators
- b. Obtaining informed consent: study coordinator, PI, co-investigators
- c. Providing on-going information to the study sponsor and the IRB: study coordinator
- d. Maintaining participant's research records: study coordinator, co-investigators
- e. Completing physical examination: co-investigators, PI, bedside nursing staff
- f. Taking vital signs, height, weight: nursing staff
- g. Drawing / collecting laboratory specimens: N/A
- h. Performing / conducting tests, procedures, interventions, questionnaires: nursing staff, co-investigators, principal investigator, study coordinator
- i. Completing study data forms: study coordinator, co-investigators
- j. Managing study database: co-investigators, study coordinator

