2. Patient assessment scales collected by nursing staff will be stored in a secure, locked location until collected by study staff. All data collected will be recorded using the KU RedCAP database. Study subjects will be deidentified in the RedCAP database.
3. subjects will not be identifiable directly and will be coded.
4. The study coordinator will have access to the code.
5. Patient medical record number will be linked to the code, and this will be used to identify study subjects during data collection.
6. Data will be stored on the secure KU RedCAP database.

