7. N/A
8. N/A

B. Sample / Specimen Collection: N/A

C. Tissue Banking Considerations: N/A

D. Procedures to protect subject confidentiality: Patients will be identified by nursing staff as enrolled in the study to collect the post-operative pain scale assessments. Nursing staff are experienced in maintaining patient confidentiality as this is an expectation with all levels of care they provide. Following the data collection process, the study subjects will be deidentified to maintain their confidentiality.

E. Quality Assurance / Monitoring

1. Data that is collected will be self-reported from patients or collected as objective data from the medical record. No subjective assessments will be done by study team members. There is a chance that study subjects could intentionally falsify their pain scores for secondary gain, for example, to receive more narcotic pain medications. To limit this potential, we will not be including patients in the study who have ongoing opioid use for chronic pain or abuse prior to admission.
2. There are no plans for third party monitoring of this study.

V. Data Analysis and Reporting

- A. Statistical and Data Analysis:** Differences between groups will be assessed using Chi square test for categorical variables and Student's t test for two means. Confidence intervals will be calculated to 95% and a p value of less than 0.05 will be considered statistically significant. Final statistical analysis will be conducted by statistician. Interim analysis is planned for at the half way point of the study (20 patients completed). Interim statistically analysis will be conducted by Co-Investigators.
- B. Outcome:** We expect that the experimental group will have decreased pain scores compared to the control group. We estimate a 2 point difference in pain scores for the STSG donor site and that this difference will occur at 1, 2 and 3 days post-op. We expect that opioid consumption and time to first opioid dose will also be decreased in the study group. Our power analysis calculation based on pain score decrease aims to enroll 40 patients in the study and this is our anticipated study end point.
- C. Study results to participants:** Study subjects may submit a written request to receive study results after completion of the study. If requested, results will be mailed to the study subject after completion of data analysis.

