Appendix III: Data collection From Chart Review

Age at time of surgery:

Gender:

Race:

Total Burn TBSA:

Deep partial thickness/ full thickness burn percentage:

Time to first opioid from minutes post-op following completion of post-operative recovery period:

First opioid dose:

First opioid route:

Total opioid administered in morphine equivalents for 72 hours post-operatively:

Non-opioid adjunct medication administration:

Anesthesia occurrences in first 72 hours post-op:

Time of donor site dressing open to air:

Time of first donor site dressing change:

[figure not shown]
Prior to admission opioid use:

Donor site size:

Donor site location:

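### Nothing in the plan hides the arm from whoever abstracts the opioid data, and the start of time to first opioid is not fixed, so a modest, cheaply removed opening for observer bias remains

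*Combined protocol and SAP*

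**What the plan says.** **Who does what.** Protocol II.K.1 says that study personnel may take part in procedures that include "patient consent, assignment of study group, and accessing of the patient's medical record to obtain information related to opioid administration". This is one undivided staff category, and the wording is permissive. II.K.2.i adds "Completing study data forms: study coordinator, co-investigators", and the same roles appear there for eligibility, consent and the database. No item in II.K.2 allots assignment of the arm to a particular role.

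**Who is blinded.** II.C.2 states "Only subjects will be blinded to their randomization group" and "Study subject number will be linked to their randomization group". IV.A says "The study coordinator will have access to the code" and uses the link from medical record number to code to find subjects during data collection. De-identification in IV.A and IV.D concerns identity; it is not said to hide the arm.

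**What is abstracted.** Appendix III lists "Time to first opioid from minutes post-op following completion of post-operative recovery period", the dose and route of the first opioid, and the 72-hour total in morphine equivalents. II.E.2.d adds daily use.

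**The plan's assurance.** IV.E.1 describes the data as patient-reported or objective chart data and says "No subjective assessments will be done by study team members".

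**The concern.** Opioid consumption is specific aim b, and time to first opioid is a planned group comparison in II.B. Both are derived from the chart by people who may know the arm, under a stated expectation (II.F.5.a, V.B) that opioid use will be lower with liposomal bupivacaine. Where a rule is missing, a person who knows the arm can settle a borderline dose or time differently in the two groups without intending to. Blinding the patient does not guard against this, and differential decisions of this kind could not be recognized afterwards from the final dataset alone. IV.E.2 plans no third-party monitoring, so no independent check on the abstraction is named.

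**Working it through.** **1. Is the arm hidden at abstraction?** Reading II.C.2, II.K.1, II.K.2, IV.A and IV.D together, no visible text describes an abstractor unaware of the arm, duplicate abstraction or an arm-free form. The material between Appendix I and Appendix III was not available and could not be checked. The overlap of assignment and abstraction is allowed, not asserted.

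**2. How much discretion do the opioid fields leave?**

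*Time to first opioid.* Three places describe its start:
- II.B leaves out the immediate recovery from anesthesia.
- II.E.2.d begins when the subject is back in routine care after recovering from surgery.
- Appendix III combines minutes after the operation with completion of the recovery period, so it can be read as counting from either point.

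None is tied to a recorded time stamp. A dose near hand-over can be excluded as a recovery dose or counted as the first dose, and the origin of the clock can move with it.

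*72-hour total.* The window and the unit are given. Three things are not: whether recovery doses count (II.B attaches that exclusion to time to first opioid only), how opioids given around a further anesthetic are handled (Appendix III records such occurrences), and which conversion table applies. An unspecified table biases the comparison only if it is applied differently by arm.

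Drug, dose, route and time of each charted administration are otherwise a matter of transcription. Time to first opioid is therefore the more exposed outcome.

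**3. The plan's own figure.** II.C.3 gives a difference of 2, SD 2.5, 80% power and 25 per group. With two-sided alpha 0.05 (sidedness is not stated):

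n = 2 × (1.960 + 0.842)² × (2.5/2)² = 2 × 7.85 × 1.5625 = 24.5, so 25 per group.

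The figure reproduces. It concerns pain scores and does not bear on opioid abstraction. V.B gives a total of 40 instead of 50, so both 25 and 20 per arm are used below.

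**4. Illustration of consequence.** The documents contain no opioid SD, no proportion of borderline doses and no hand-over timing, so the shift b (in SD units, one arm relative to the other) is an assumption. With no true effect, the planned two-sample t statistic follows a noncentral t distribution with 2n − 2 degrees of freedom and noncentrality b × √(n/2). The false-positive rate is the probability that it falls outside the two-sided 5% limits.

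| Assumed b (SD) | Noncentrality, n = 25 | Rejection, n = 25 | Noncentrality, n = 20 | Rejection, n = 20 |
|---|---|---|---|---|
| 0 | 0 | 5.0% | 0 | 5.0% |
| 0.1 | 0.354 | 6.4% | 0.316 | 6.1% |
| 0.2 | 0.707 | 10.7% | 0.632 | 9.5% |
| 0.3 | 1.061 | 18.0% | 0.949 | 15.2% |

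A shift of 0.1 SD matters little; 0.2 SD about doubles the error rate. The table shows what an assumed shift would do. It does not estimate what this abstraction would produce.

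**The case against.** The best case for the plan has four parts.

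- **The chart is objective.** Doses and times are recorded when given, and the team copies them. This largely stands, and IV.E.1 is a real mitigation. A reader might infer that the opioid outcomes are subjective and that IV.E.1 is simply wrong. The documents do not support that: the discretion is confined to the start of the clock, the boundary doses and the conversion.
- **II.K.1 lists tasks for a category of staff.** A reader might infer that whoever assigns the arm also reads the opioid data. The text says only that study personnel may be involved, and II.C.1 has a computerized generator produce the allocation. What stands against the plan is that the overlap is permitted and nothing prevents it.
- **Written definitions would do most of the work.** With one recorded time zero and one conversion table, little is left for a masked abstractor to protect. This is largely right, and those definitions belong in the fix. Masking then covers the remaining doubtful cases at little extra cost.
- **A larger route stays open.** Because only subjects are blinded, treating staff may know the arm when opioids are given, and masked abstraction cannot undo that. This stands in full. It limits what the fix achieves but is no reason to leave the smaller opening.

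There is also a practical objection: IV.A uses the code link to find subjects, so an abstractor without the code cannot open the chart. The fix must therefore say who prepares the listing.

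**Conclusion.** The point holds as a modest gap that is cheap to close. The plan allows the arm to be known when the opioid outcomes are derived, and it leaves the start of time to first opioid without an operational definition. Time to first opioid carries most of the exposure; the 72-hour total carries less, through boundary doses and conversion.

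The size of any bias is unknown. A reader might take 6% to 18% as the trial's false-positive rate, but that range follows only from an assumed shift of 0.1 to 0.3 SD, which nothing in the documents anchors. It also assumes a two-sided test, a constant shift on an outcome suited to the t test, and no allowance for the interim look. Nor should it be applied equally to both outcomes. The pain comparison, on which the sample size rests, is not affected by this point.

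**What to change.** Amend II.C.2, II.K.1 and IV.A, with matching wording in II.B, II.E.2.d and Appendix III, to state the following.

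1. **Export.** The code holder exports, by subject number, every charted opioid administration (drug, dose, route, time) and the recorded recovery hand-over time. No doses are selected, and the listing carries no arm, operative note or study-drug line.
2. **Definitions.** One time zero, tied to a recorded time, is fixed in advance, with one rule for recovery doses and for doses around a further anesthetic, and one morphine-equivalent conversion table.
3. **Derivation.** An existing team member who did not assign the arm, took no part in the operation and holds neither the code nor the arm link derives time to first opioid and the daily and 72-hour totals.
4. **Merge.** The arm is added only after these fields are locked. Because V.A has co-investigators run an interim analysis at 20 completed patients, the fields for those patients are locked before that look, and the person deriving them does not run it.

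The cost is protocol wording, a division of tasks among roles already named and a little more work to prepare the listing. Sample size and patient burden do not change. The change does not remove bias from unblinded treating staff deciding when opioids are given; the report should state that limitation.

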3. We anticipate a reduction in pain scores by 2 points with SD 2.5 in the experimental group. Power analysis for 80% power yields 25 patients per group. We will aim to enroll a total of 50 patients, 25 in each group.

D. Subject Criteria (See Vulnerable Populations appendix, if applicable):

1. Inclusion criteria: State the criteria for inclusion in the study in a specific and detailed manner.
 - E. Age \geq 18 years, English or Spanish speaking, Burn injury with the following parameters: $\leq 20\%$ TBSA partial thickness, $\leq 5\%$ TBSA deep partial or full thickness, first skin autografting procedure for hospitalization, donor site anterior or lateral thigh
2. Exclusion criteria: State the criteria for excluding potential subjects from the study in a specific and detailed manner.
 - E. Chronic pain syndrome on opioid pain medications at baseline, $>20\%$ TBSA partial thickness burn, $>5\%$ TBSA surgical area of burn injury (deep partial or full thickness injury), pregnant women, age < 18 , not first skin autografting procedure during hospitalization, allergy to lidocaine or other local anesthetics, burns to anterior thighs, inability to give informed consent
3. Withdrawal/Termination criteria: Include the specific circumstances in which the subject's participation will be terminated by the investigator. Include any necessary safety precautions to be applied to those who withdraw (tapering drug doses, evaluative x-ray, etc.)
 - E. Serious adverse reactions to lidocaine or liposomal bupivacaine including cardiac event, arrhythmia, seizure, anaphylaxis, and loss of limb. Subjects who experience these reactions will be medically stabilized and undergo standard work-up based upon symptoms. The subject will be unblinded and the medication administered will be documented in their medical record as an allergy. They will be withdrawn from the study and the adverse reaction will be reported to the IRB within 24 hours.
4. Clarify whether a study subject may participate in another research study while participating in this research study.
 - E. Subjects may participate in additional research studies as long as study protocols do not interfere with one another. For example, subjects may not be enrolled in a study comparing experimental pain management or alternative methods of skin autograft harvest.

E. Specific methods and techniques used throughout the study

1. Laboratory tests: No laboratory specimens will be required for participation in this study.

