L. Assessment of Subject Safety and Development of a Data and Safety Monitoring Plan

- 1. Elements of the plan include:
 - a. Persons/groups who will review the data (study team; independent safety monitor, data monitoring committee or formal DSMB): The study team including the study coordinator will routinely monitor the study data to assess for patient safety issues or unanticipated patient events.
 - b. Data/events that will be reviewed: adverse events, pain assessment, opioid usage
 - c. Frequency of review: A formal review will be conducted at the midpoint of the study; additional reviews can be completed as needed in the event of any unanticipated event or concerns from study team members
 - d. Types of analyses to be performed: statistical analysis of data to determine if endpoints of study have been met.
 - e. Safety-related triggers that would cause the PI to stop or alter the study: presence of significant adverse events such as loss of limb or death; significant increase observed in pain and opioid usage in experimental group compared to control group
- 2. Adverse Events that occur during the course of the study will be documented. For each recorded event, the documentation will include the event's onset and resolution date (if the event has resolved), the frequency and severity of the event, a summary of any action taken as a result of the event (both in regard to any treatment given and to any change in dosing with the test article), and an assessment of the event's relationship to the test article.
 - a. Non-serious Adverse Events
 - 1. A non-serious adverse event is defined as a change from baseline (pre-treatment) in a subject's medical health that is not life-threatening, does not require hospitalization, does not prolong a current hospitalization, and is not disabling. Non-serious adverse events that may occur with the use of liposomal bupivacaine according to the FDA are hypoesthesia, hypotension, pain, drug ineffectivity, nausea, bradycardia, drug interactions due to medication error, nerve palsy, and erythema. These events all

occur at rates less than or equal to other medications marketed for similar indications, including lidocaine.

b. Serious Adverse Events- Serious Adverse Events that are suspected to be related to the test article and are unexpected (not identified in the product-package insert), will be reported to IRB and to the manufacturer of the test article within 24 hrs of the investigator's knowledge.

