- **Not Related** – An event is considered to be not related to the use of the test article when the event is DEFINITELY UNRELATED or UNLIKELY to have any relationship to the use of the test article.
- **Related** – An event is considered to be related to the use of the test article when there is a POSSIBLE, PROBABLE, or DEFINITE relationship between the adverse event and the use of the test article.

For example, a single occurrence of an event that is uncommon and known to be strongly associated with drug exposure (e.g., seizure, cardiac arrhythmia) has a reasonable possibility of association with the test article. One or more occurrences of an event that is not commonly associated with drug exposure, but is otherwise uncommon in the population exposed to the test article, may have a reasonable possibility of association. Adverse events which are known to be common in the population under study would require additional evidence (e.g., strong temporal relationship, recurrence on re-challenge, unusual severity, and/or increasing frequency) before being considered possibly related.

Adverse events which are known to occur frequently in the population defined by this protocol include: wound infection, pain and itch of the wound, and contact dermatitis.

- d. Follow-up of Subjects with Adverse Events: For subjects who are experiencing ongoing unresolved adverse events at the time of their study completion or early discontinuation from the study, appropriate follow-up visits in order to determine the outcome of the event will be scheduled.
3. Subjects who experience an adverse events will be medically stabilized and undergo standard work-up based upon symptoms. The subject will be unblinded and the medication administered will be documented in their medical record as an allergy. They will be withdrawn from the study and the adverse reaction will be reported to the IRB within 24 hours as per procedure outlined above.

III. Subject Participation

A. Recruitment:

1. Patients will primarily be recruited in the KU Hospital Burn Unit. Rarely, patients may be recruited prior to their admission to the Burn Unit in either the KU Emergency Department or KU Burn and Wound Clinic prior to proceeding to the operating room. No recruitment will take place at locations outside of KUMC.

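### As written, II.L.3 unblinds, charts a drug allergy for and withdraws any subject with an adverse event, contradicting II.D.3, which reserves these steps for serious drug reactions

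*Combined protocol and SAP*

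**What the plan says.** Three places in the combined protocol and SAP govern what happens to a subject after an adverse event or reaction.

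- **II.L.3** (end of the safety monitoring section) opens: "Subjects who experience an adverse events will be medically stabilized and undergo standard work-up based upon symptoms". It continues: "The subject will be unblinded and the medication administered will be documented in their medical record as an allergy". It ends with withdrawal and an IRB report: "They will be withdrawn from the study and the adverse reaction will be reported to the IRB within 24 hours as per procedure", followed by a pointer back to the reporting procedure earlier in the section.
- **II.D.3** (withdrawal/termination criteria) names its trigger as "Serious adverse reactions to lidocaine or liposomal bupivacaine including cardiac event, arrhythmia, seizure, anaphylaxis, and loss of limb". Stabilisation, work-up, unblinding and the allergy entry follow, and then: "They will be withdrawn from the study and the adverse reaction will be reported to the IRB within 24 hours".
- **II.C.2** (blinding) says "Blinding may be broken if the subject experiences an adverse reaction to the medication utilized for their group", so that the subject knows not to receive that drug in future. The same item states: "Only subjects will be blinded to their randomization group".

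Two further items bear on the reading. II.L.2.d arranges follow-up visits for subjects whose adverse events are unresolved when they complete the study or leave it early. II.L.2.a lists non-serious adverse events that include nausea, erythema, pain and lack of drug effect, and II.L.2.c names wound infection, wound pain and itching, and contact dermatitis as frequent in this population.

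Neither II.D.3 nor II.L.3 says whether the 72-hour pain and opioid collection continues after withdrawal. V.A names no analysis population.

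**The concern.** Adverse event is the broad term in section II.L. The items before II.L.3 divide such events into serious and non-serious, mild to severe, and related or not related. II.L.3 then uses the broad term with none of these limits and makes the consequences mandatory.

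Three things would follow if staff applied it as it stands, whatever the event rate:

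1. A subject with nausea, or with a wound infection unrelated to the injection, would leave with a local anaesthetic allergy on record. That entry would be wrong and could affect later care.
2. The subject would be told the allocation. Subjects are the only blinded party, and the main outcome is their own pain rating.
3. The subject would be withdrawn, and the remaining pain scores could be lost, from a trial that plans 25 subjects per group in II.C.3 and states no allowance for loss.

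**Working it through.** **Step 1. Set the rules side by side.**

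| | II.L.3 | II.D.3 | II.C.2 |
|---|---|---|---|
| Trigger | an adverse event, unqualified | serious adverse reaction to either drug | adverse reaction to the assigned drug |
| Unblind | required | required | permitted |
| Allergy entry | required | required | not mentioned |
| Withdraw | required | required | not mentioned |
| IRB report in 24 hours | required | required | not mentioned |

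The actions in II.L.3 and II.D.3 match; the triggers do not. That is a direct contradiction. II.L.3 goes beyond II.C.2 in two ways: it drops the link to the drug, and it turns a permission into a requirement. II.C.2 and II.D.3 are compatible with each other.

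**Step 2. Run events through the rules.**

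| Event | II.L.3, literally | II.D.3 | II.C.2 |
|---|---|---|---|
| Seizure attributed to the drug | unblind, allergy, withdraw | same | may unblind |
| Nausea | unblind, allergy, withdraw | no action | may unblind only if a reaction to the drug |
| Unrelated wound infection | unblind, allergy, withdraw | no action | no |

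The rules give the same answer only for serious drug reactions.

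**Step 3. Check II.L.2.d.** It assumes that some subjects with unresolved events reach completion, which a literal II.L.3 would prevent. It also covers early discontinuation, so the clause still works. The tension is by implication only.

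**Step 4. Look for signs of intent.** II.L.3 moves from an event to a reaction, requires an allergy entry, and points back to a 24-hour procedure that II.L.2.b sets out for serious events. All three suggest that serious drug reactions were meant. None of them limits the trigger sentence.

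**Step 5. Size, as a conditional illustration only.** Inputs from II.C: difference 2, SD 2.5, 1:1 allocation, Student's t test, alpha 0.05 (two-sided assumed), 80% power.

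The plan's own figure reproduces: n per group = 2 × (1.960 + 0.842)² × 2.5² / 2² = 2 × 7.85 × 6.25 / 4 = 24.5, rounded up to 25. The exact t test needs 25.5, that is 26, and 25 per group gives 79.1% power.

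Now suppose that withdrawn subjects contribute nothing and that loss is unrelated to pain. The standardised difference is 2 / 2.5 = 0.8 and the noncentrality is 0.8 × √(n/2):

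| Lost of 50 (assumed) | n per group | Noncentrality | Exact power |
|---|---|---|---|
| 0 | 25 | 2.83 | 79.1% |
| 5 | 22.5 | 2.68 | 74.6% |
| 10 | 20 | 2.53 | 69.3% |

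No document supports any of these loss rates. They overstate the cost if scores collected before withdrawal are kept, or if opioid use is still taken from the medical record.

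**The case against.** The strongest reply is that this is a dropped qualifier and not a competing rule. II.L.3 repeats II.D.3 almost step for step, II.D.3 sits under the heading that governs withdrawal, and the cross-reference in II.L.3 leads to the procedure for serious events. Nobody chose to withdraw subjects for nausea. This stands as an account of intent, and it is why the point is minor. It does not rescue the text: staff who read the safety section alone would find a mandatory rule with a wider trigger.

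A reader might go further and infer that, because pain and lack of effect are listed as adverse events, II.L.3 would remove high-pain subjects and bias the pain comparison. The documents do not support that. II.L.1.b keeps the two apart: "Data/events that will be reviewed: adverse events, pain assessment, opioid usage". Donor-site pain is the outcome, scored on a schedule in every subject (II.E.2.d). II.L.1.e deals with worse pain through a between-group trigger to stop or alter the study. II.L.2.c asks for more evidence before a common event is called possibly related. That last guard concerns causality, which II.L.3 does not mention, so it weakens the pain reading without excluding it.

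Simulations of the pain pathway rest on assumed values throughout: control mean 5, withdrawal cutoffs of 6 to 8, correlation between days of 0.5 or 0.7, and every trigger rate. If 5% of qualifying scores led to withdrawal in both arms, the day 3 difference would be 1.96 to 1.99 in place of 2, with power 77% to 79%. With no true effect and rates of 5% and 10% in the control and experimental arms, the type I error stays at about 5%. At modest use the effect is negligible.

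A reader might also infer that all the rules conflict with one another. They do not, as Steps 1 and 3 show.

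**Conclusion.** Wrong as written; minor. The firm finding is that the trigger in II.L.3 contradicts that in II.D.3 and goes beyond II.C.2. This rests on the wording alone and needs no assumption. The harms that follow from literal use are inaccurate allergy entries, needless unblinding of the only blinded party, and lost self-reported pain data after minor or unrelated events.

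The effect on power or bias cannot be quantified, because the documents give no adverse event rate and do not say how often the rule would be used. It is small if the rule is rarely applied. The power figures show only what an assumed loss would cost, and the conclusion does not depend on them.

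**What to change.** 1. In II.L.3, replace the trigger with: *a serious adverse reaction to the study drug as listed in II.D.3*. Keep the II.C.2 option to unblind for a drug reaction that bars future use. State that donor-site pain or lack of effect does not by itself trigger unblinding, an allergy entry or withdrawal.
2. The study drug is given once, during the operation, so stopping treatment has no meaning here. In both II.D.3 and II.L.3, replace withdrawal from the study with continued 72-hour pain and opioid collection where the subject is able and consents.
3. State in V.A that these subjects are analysed in their randomised group.

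The cost is a few sentences in three sections and a few extra pain scales of about a minute each. The downside is that some retained pain scores may come from subjects who know their allocation.
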